### **B1. PURPOSE OF PROTOCOL**

The purpose of the protocol is to evaluate the effect of sclerotherapy on fistula and sinus tract involvement using hypertonic saline injections in fistulas and sinus tracts in subjects with hidradenitis suppurativa

### **B2. SIGNIFICANCE AND BACKGROUND FOR THE STUDY**

Hidradenitis Suppurativa (HS) is a chronic suppurative disease characterized by firm, tender, inflammatory, red nodules that often evolve into fluctuant and malodorous painful abscesses, fistulas, and non-healing sores. Rupture of the lesion, suppuration, formation of sinus tracts and scarring frequently occurs. It has been estimated to affect up to 4% of the population, affecting women more commonly than men. A study performed in 2007 showed that the disease can cause significant morbidity, especially among patients who have an early onset of disease, long duration and continuous evolution. Proposed etiologic factors include follicular occlusion, bacterial infection, genetics, host defense defects, hormonal influences, cigarette smoking, and irritants. Although the current belief is that the primary defect is occlusion of the terminal parts of the follicular acroinfundibulum^5 and recent genetic information supports this hypothesis, the apocrine milieu is likely to play a meaningful role in the disease because it primarily affects apocrine gland-containing regions such as the axillary, inguinal and perineal areas. Importantly, the disease also responds well to complete excision of these apocrine gland-containing sites. While this approach is substantially disfiguring, requiring large areas of excision, it also typically results in a cure in the region excised, while other areas will remain active.

In order to classify HS the Hurley classification and the Sartorius scoring system are used, both rely on clinical data, which may be inaccurate because of the difficulty in assessing the extensiveness of the lesions beneath the skin surface. This can lead to underestimation of severity. Ultrasound has also been used as a low-invasive and safe method for evaluating the lesions of HS.

One persistent problem for many patients is the continued presence of draining fistulas and sinus

### B3. DESCRIPTION OF RESEARCH PROTOCOL

#### A. Study Design – Overview, Methods, Procedures

##### Study Design and plan:

The design of this study is a single center, single-blinded clinical research treatment study. This clinical study will be conducted at Beth Israel Deaconess Medical Center in Boston (the study was previously conducted at MGH and is currently being conducted at both institutions through Cede Review with MGH as the overseeing IRB and BIDMC). All subjects with a signed informed consent will be screened to ensure they meet all inclusion criteria and do not meet the exclusion criteria. After enrolment, the duration of the study is approximately 8 weeks, involving 3 or 4 visits. A schematic overview of the main procedures during each visit is illustrated in Appendix 2.

The clinical effect of the hypertonic saline treatment will be evaluated with Physician and patients Assessments at week 2 (t=2), week four (t=4) and week 8 (t=8) and compared with the first visit (baseline) (t=0). If necessary, subjects will be eligible to receive another hypertonic saline injected in week 2 and/or week 4, with a maximum of three injections. Simultaneously improvement will be assessed by ultrasound if possible, using the Philips Lumify Ultrasound Device, and by patients using HS Improvement Assessments. Pain and stinging during treatment sessions will be monitored using numeric rating scales (NRS). For monitoring quality of life the DLQI will be used.

Prior to performing any study related procedures, the investigator will discuss with each subject the nature of the study, its requirements and its restrictions. A written informed consent form will be obtained from each participant prior to any procedure. Each subject with a signed informed consent form will be screened at the first visit, to ensure all the inclusion criteria are met and none of the exclusion criteria. Medical history and demographic information will be taken. Patients will have their medication reviewed and undergo a full HS examination, including lesion counts, Hurley staging and target site assessment. Target HS area(s) will be digitally photographed and be imaged with ultrasound. The duration of the study is approximately 8 weeks, involving a minimum of 3 and a maximum of 4 visits. In case of an adverse event or disease progression, patients are instructed to call and/or visit the clinic. An overview of the exact procedures during each visit can be found in the chart

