##### Study Table (Chart with Study Procedures)

Activity (timeline)	0 week (Baseline)	2 Week	4 Week	Week 8
Subject Information and Informed Consent	✓			
Eligibility Criteria	✓			
Medical History	✓			
Prior and concomitant therapy	✓			

Review and document pregnancy avoidance with females of child bearing age	✓			
23.4% Hypertonic Saline Injection	✓	✓	✓	
Urine Pregnancy Test (For all females of childbearing age)	✓	✓	✓	
Ultrasound (to locate the tracts)	✓			✓

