**Secondary study parameter(s)**

Hence the small patient group in this pilot study, no power is expected from statistical analysis. Therefore all outcomes will be assessed by using descriptive statistics.

The clinical efficacy will also be measured using the following outcomes:

- Measuring the length and the lumen of the fistulas using ultrasound if possible. Since this variable is highly dependent on investigator and experience with ultrasound, descriptive statistics will be used to present this variable.

The patient reported outcomes:

- HS Improvement assessment: this is a continuous variable and depending on the date

distribution a one way ANOVA, a Kruskal Wallis or a Wilcoxon rank sum test will be performed for analysis.

- NRS to assess pain and stinging: continuous variable. Per individual a percentage improvement will be calculated as a main outcome.
- DLQI: continuous variable. this is a continuous variable and depending on the date distribution a one way ANOVA, a Kruskal Wallis or a Wilcoxon rank sum test will be performed for analysis.

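### Does the undefined single-blinded label mean that the baseline and week 8 ultrasound scans must be read masked to visit?

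*Combined protocol and SAP*

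**What the plan says.** The design sentence in Section B3.A (Study Design and plan) reads: "The design of this study is a single center, single-blinded clinical research treatment study". It is the only mention of blinding in the available text. The next sentence of that section says that the study "is currently being conducted at both institutions", and the Sample Size Justification (B3.B.a) places 14 of the 20 subjects at BIDMC.

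The same section describes one treatment, with outcomes at weeks 2, 4 and 8 "compared with the first visit (baseline) (t=0"). The primary outcome in B3.B.b is the physician and patient assessments.

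Ultrasound appears in three places:
- Section B3.A: "Simultaneously improvement will be assessed by ultrasound if possible".
- The Study Table: a row labelled "Ultrasound (to locate the tracts"), ticked at baseline and week 8.
- Secondary study parameter(s): "Measuring the length and the lumen of the fistulas using ultrasound if possible". The reason given for presenting it descriptively is "Since this variable is highly dependent on investigator and experience with ultrasound".

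The opening paragraph on secondary parameters also says, on account of the small group: "Therefore all outcomes will be assessed by using descriptive statistics".

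**The concern.** A blinding claim tells readers that some source of bias has been controlled. Here nothing visible stands behind it. With no comparator, sham or randomisation there is no allocation to conceal, and patients who know they were injected rate themselves. The one thing that could still be hidden is the visit, from someone reading an image.

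Ultrasound looks like the natural place for that. A before-and-after pair is already scheduled, and the plan concedes that the measurement depends on who makes it. A reader who knows which scan is the later one may measure the tract as shorter or narrower because improvement is expected. Descriptive statistics would pass that bias on, not remove it. At stake is whether any efficacy result from the pilot could fairly be reported as blinded.

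**Working it through.** The plan gives no figure to reproduce: it has no power calculation, effect size or measurement error for ultrasound. The check is therefore mainly a comparison of the text.

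**1. Could the label refer to treatment?** The Study Table has one injection row and no control injection, and B3.A compares each subject with baseline. No masking of treatment is evident. The label can only refer to an assessor's knowledge of the visit, or it is a mistake.

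**2. Does anything in the analysis depend on it?** B3.B.b names no masked assessor for any outcome. It gives candidate tests for the physician and patient assessments, the HS improvement assessment and DLQI. Ultrasound is given none. No planned test, threshold or stopping decision uses length or lumen, so removing the label or giving it content would alter no analysis.

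**3. What would a masked reading need?** At most 20 subjects × 2 visits = 40 image sets, fewer because scans are done only where feasible. The workload is small. But it requires images to be archived, and B3.A says only that target areas are imaged. It also requires a reader who neither scanned nor treated the subject, and no such person is described. The study is already running, so any scan taken without a stored image could not be included.

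**4. What would it remove?** Only expectation at the reading step. The operator at week 8 knows the visit while choosing the tract, the plane and the frame. The plan's remark about investigator and experience covers acquiring the scan as well as reading it. The primary physician assessment stays unmasked. Regression to the mean and natural fluctuation are untouched.

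**5. Does two-site conduct make it worse?** BIDMC has 14 subjects and 20 − 14 = 6 are elsewhere, so two or more readers are likely across the study. The outcome, however, is change within a subject. Nothing suggests that one subject's two scans are split between sites.

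**6. Can the bias be sized?** Only by inventing a rule. Suppose no tract changes and a reader must say which scan of each pair shows the smaller lumen, choosing week 8 with probability p. Then P(X ≥ k) = Σ C(n, j) p^j (1 − p)^(n − j), summed over j from k to n.

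| p | n = 20, k = 15 | n = 12, k = 10 |
|---|---|---|
| 0.50 (masked) | 21,700 / 1,048,576 = 0.0207 | 79 / 4,096 = 0.0193 |
| 0.55 | 0.0553 | 0.0421 |
| 0.60 | 0.1256 | 0.0834 |
| 0.70 | 0.4164 | 0.2528 |

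The arithmetic is right, but the forced choice, the cut-offs and the leans are all assumed. The plan measures length and lumen and describes them. It does not count pairs against a cut-off. The table also assumes one result per subject, whereas the inclusion criteria allow several tracts. These are error rates of a rule the plan does not contain and do not measure any defect in it.

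**The case for a change.** The best argument for acting is that the label promises a protection that no visible procedure delivers, and that the remedy is cheap. Section B2 says that clinical scoring may be inaccurate because disease beneath the skin is hard to see, so ultrasound is the outcome best placed to add objectivity. The pair of scans is already scheduled, 40 readings is little work, and deleting the word costs nothing.

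Part of this stands. The label is undefined in the available text, and a report that repeated it unexplained would mislead. The words single center are likewise at odds with the text that follows them. Expectation at reading is a real source of bias, and descriptive reporting does not cure it.

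The step from there to a new reading procedure does not stand. The resources it needs are not in the plan. It would protect a supportive outcome and leave the primary one as it is. Calling the result blinded when the person holding the probe knew the visit would replace an unsupported label with a partly supported one. Deleting or defining the word alters no procedure, dataset or result.

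**Conclusion.** No change to the plan follows. The design label is loose wording, and the missing reading rule concerns a secondary, descriptive measure whose limits the plan already admits. An analyst would treat the study as what the text describes: a single-arm, before-and-after pilot of 20 subjects, with ultrasound summarised and not tested, and without claiming blinded efficacy unless a masked assessor can be named. The effect on planned tests is nil, since none uses ultrasound. No size can be given for bias in the descriptive figures, because the documents hold no information on reader error.

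Two assumptions support this. First, the write-up presents the ultrasound changes as uncontrolled and investigator-dependent, in line with the plan's own caveat. Second, the unread text contains nothing that alters the picture. Appendix 2 and the end of Section B2 were not available, and the Study Table appears incomplete, with no rows for the physician assessment, NRS or DLQI. A definition of the blinding could sit there. If it does, the concern falls away altogether. If it does not, the wording slip remains a wording slip.

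### The only stated timing for the pain score is during injections, yet its percentage improvement serves as an efficacy outcome; on that timing, one-injection patients and week 8 have no value

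*Combined protocol and SAP*

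**What the plan says.** Three places in the combined protocol and SAP bear on this.

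- **B3.A, Study Design and plan.** The sentence on timing is "Pain and stinging during treatment sessions will be monitored using numeric rating scales (NRS". The same paragraph makes later treatment conditional: "If necessary, subjects will be eligible to receive another hypertonic saline injected in week 2 and/or week 4, with a maximum of three injections". It times the physician and patient assessments separately, at "week 2 (t=2), week four (t=4) and week 8 (t=8) and compared with the first visit (baseline) (t=0".
- **Study Table.** The row "23.4% Hypertonic Saline Injection" is ticked at baseline, week 2 and week 4, and not at week 8.
- **B3.B.b, Secondary study parameter(s).** The lead-in is "The clinical efficacy will also be measured using the following outcomes". Ultrasound follows, then a sub-list of patient-reported outcomes that contains "NRS to assess pain and stinging: continuous variable" and "Per individual a percentage improvement will be calculated as a main outcome". Neither a reference score nor a follow-up time is given for that percentage.

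**The concern.** A percentage improvement needs two scores per patient: a reference and a later one. The one timing that the protocol states ties the score to the act of injecting. Whether a second score exists therefore depends on whether a second injection is given, which is decided after baseline.

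Two things are at stake. First, the set of patients who contribute an improvement would be fixed by a treatment decision made during the trial and not by enrolment. No summary statistic or choice of reference value can recover scores that were not taken. Second, a score taken during injection measures how much the procedure hurts. A fall between the first and second injection could reflect the procedure or habituation as much as any relief of disease pain. The background section describes the lesions as painful, so readers will look to this outcome for symptom relief.

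**Working it through.** The plan has no figure of its own to reproduce. The sample-size section gives 20 subjects in total and says that no calculation applies. The check is to follow the stated timing through the visit schedule and count.

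**Inputs**
- N = 20 (Sample Size Justification).
- Stated scoring occasions: injection sessions (B3.A).
- Possible injection sessions: baseline, then week 2 and/or week 4 where judged necessary, at most three in all (B3.A and the Study Table).
- Share of patients not re-injected, s: not in the documents, so it is varied as an assumption.

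**Step 1: scores per patient under the stated timing**

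| Injections received | Scores available | Improvement computable? | Score at week 8? |
|---|---|---|---|
| 1 (baseline only) | 1 | No | No |
| 2 (baseline plus week 2 or 4) | 2 | Yes | No |
| 3 (baseline, weeks 2 and 4) | 3 | Yes | No |

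**Step 2: patients without a value**

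Number without a value = N × s, and number with a value = N × (1 − s).

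| Assumed s | Without a value | With a value |
|---|---|---|
| 0% | 20 × 0 = 0 | 20 |
| 25% | 20 × 0.25 = 5 | 15 |
| 50% | 20 × 0.50 = 10 | 10 |
| 75% | 20 × 0.75 = 15 | 5 |
| 100% | 20 × 1 = 20 | 0 |

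The number with a week-8 score is 0 in every row, because no injection is ticked there.

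**Step 3: what the available values measure**

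B3.A pairs pain with stinging and places both in the treatment session. The secondary-parameter section uses the same pair. Section B5 lists stinging and injection-site pain as the more common risks in the consent form. Read together, these describe a procedural score. Even with s = 0, where nobody is left out, the outcome would be change in injection pain between sessions, ending no later than week 4.

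**The case against.** The strongest reply is that the documents leave the measurement under-specified without showing that it is wrongly placed. B3.A says that pain during sessions is scored; it does not say that pain is scored at no other time. The secondary-parameter entry carries no such limit, and planning a percentage improvement for each individual implies repeated scores. The study table cannot settle it. As supplied, it has no NRS row, but it also has no rows for the DLQI, the photographs, or the physician and patient assessments, although B3.A gives those assessments explicit weeks. Appendix 2, which B3.A cites for an overview of the visits, was not in the text available. This stands. A reader might infer that one-injection patients can never have a pain change and that nobody is scored at week 8. The documents support that only if the stated timing is the whole of the collection.

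A second reply is that the score may be meant for tolerability. It sits in a patient-reported sub-list after the efficacy lead-in, and the trial is described as a feasibility and tolerability pilot. On that reading, scoring at injections is right and the fault lies in the wording about improvement. This stands in part: the during-injection score is worth keeping. But the sub-list still falls under the efficacy lead-in, and the plan asks for a percentage improvement as a main outcome.

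A third reply is that the consequence is small: this is a secondary outcome in 20 patients, to be described and not tested, while primary efficacy rests on assessments not tied to re-injection. That limits the weight of the point. It does not remove it, because a descriptive mean over a selected subset is selected too.

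**Conclusion.** The point holds in conditional form. The only timing stated in the available text is during treatment sessions, and no timepoints are named for the percentage improvement. If scores are collected as stated and nowhere else, the improvement is missing for 20 × s patients and there is no pain score at week 8. Those with a value are chosen by a post-baseline judgement, and the quantity is procedural pain. The count runs from 0, if all are re-injected, through 5, 10 and 15 at s of 25%, 50% and 75%. The share s is an assumption throughout.

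Two stronger readings should not be drawn. A reader might infer that the patients left out are the best responders, so that the reported improvement is too low. The protocol gives no criterion for re-injection, and a partial response or a further tract could prompt it as readily as a failure to respond. A reader might also want a figure for the bias. Any such figure would need assumed reductions in disease pain in each group, and would then treat a score of injection pain as if it measured them. Neither the direction nor the size of a bias can be estimated from the documents.

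The matter is worth correcting before data collection because scores not taken cannot be recovered later. It does not touch the primary outcome.

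**What to change.** In B3.A and in the secondary-parameter section:

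1. Record a 0-10 pain NRS for the treated site at every attended visit (weeks 0, 2, 4 and 8), before any injection and whether or not one follows.
2. Make change in this score from baseline to week 8, summarised in all patients, the pain efficacy outcome. State how many patients contribute. If a percentage is kept, say how a baseline score of 0 is handled, since a percentage change from 0 is undefined.
3. Report the during-injection pain and stinging NRS as tolerability only, by session, with no improvement calculated from it.
4. Show both scores in the study table with their visits.

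If pain is already scored at every visit, items 1 and 4 only write down existing practice, but the text still needs to say so.

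The cost is one extra question at visits already scheduled, at most 4 per patient or 4 × 20 = 80 scores in the trial, plus the wording. No treatment rule changes.

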##### Study Table (Chart with Study Procedures)

Activity (timeline)	0 week (Baseline)	2 Week	4 Week	Week 8
Subject Information and Informed Consent	✓			
Eligibility Criteria	✓			
Medical History	✓			
Prior and concomitant therapy	✓			

Review and document pregnancy avoidance with females of child bearing age	✓			
23.4% Hypertonic Saline Injection	✓	✓	✓	
Urine Pregnancy Test (For all females of childbearing age)	✓	✓	✓	
Ultrasound (to locate the tracts)	✓			✓

**B. Statistical Considerations**

**a. Sample Size Justification:**

The total number of subjects to be studied is 20 and the number to be studied at BIDMC is 14. A sample size calculation is not applicable, for this is an early feasibility and tolerability pilot study.

**b. Data Analysis:**

**Primary study parameter(s)**

The clinical efficacy will be measured by Physician and patients Assessments. These are continuous variables and depending on the date distribution a one way ANOVA, a Kruskal Wallis or a Wilcoxon rank sum test will be performed for analysis.

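### The primary analysis leaves six baseline comparisons unranked and names tests for independent groups, although the same subjects are measured at every visit

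*Combined protocol and SAP*

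**What the plan says.** Section B3.B.b, Primary study parameter(s), states: "The clinical efficacy will be measured by Physician and patients Assessments". It treats these as continuous and says that "depending on the date distribution a one way ANOVA, a Kruskal Wallis or a Wilcoxon rank sum test will be performed for analysis". Section B3.A, Study Design and plan, sets the comparisons: "Physician and patients Assessments at week 2 (t=2), week four (t=4) and week 8 (t=8) and compared with the first visit (baseline". The same section describes follow-up as "involving a minimum of 3 and a maximum of 4 visits", and it allows repeat injections at weeks 2 and 4.

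On size, section B3.B.a states: "The total number of subjects to be studied is 20 and the number to be studied at BIDMC is 14". It gives no sample size calculation and calls the study a pilot of feasibility and tolerability. No control arm is described.

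The Secondary study parameter(s) section expects no power and says that every outcome will be handled descriptively. It then lists the same three tests for the HS Improvement assessment and the DLQI.

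Nowhere do the documents rank the two primary instruments, name a primary visit, give a significance level, or say whether one or both instruments must show improvement.

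**The concern.** There are two separate faults, and they interact.

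- **The comparison is not fixed.** Two instruments at three follow-up visits give six comparisons with baseline, and any of them could be presented as the primary result. The visits are not interchangeable: a subject may have had more injections by week 8 than by week 2, so the choice of visit changes which effect is estimated. Some subjects may also have only three visits and so not contribute to every comparison.
- **The tests do not fit the data.** All three named methods treat the visits as separate groups of people, but the same subjects are measured each time. Distribution can reasonably decide between ANOVA and Kruskal-Wallis. It cannot decide between Kruskal-Wallis and rank sum, because the first asks whether any visit differs and the second compares one pair of visits. Moving to rank sum therefore changes the hypothesis, and no pair is named.

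With about 20 subjects and no control arm, fixing the comparison in advance is one of the few safeguards available. The study plans conference abstracts and a journal article, so a selected p-value could reach print as the primary finding.

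**Working it through.** The plan states no error rate, power or effect size, so it has no figure of its own to reproduce.

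**Inputs from the documents:** 2 instruments, 3 follow-up visits, n = 20, and the three named tests.

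**Assumptions:** each test at two-sided 0.05; normal scores with equal variance; within-subject correlation r between visits of 0.3 to 0.7; correlation between instruments of 0 to 0.7.

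**Step 1: number of comparisons.** 2 × 3 = 6 pairwise comparisons. With an omnibus ANOVA or Kruskal-Wallis there is one test per instrument, so 2.

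**Step 2: ceilings if tests were independent and valid.** Six tests: 1 − 0.95^6 = 26.5%. Two tests: 1 − 0.95^2 = 9.75%.

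**Step 3: effect of ignoring the pairing.** With standard deviation σ, the difference between two visits has variance 2σ²(1 − r) per subject. A test for independent groups assumes 2σ². At r = 0.5 that is twice the true variance, so the test rejects too rarely.

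**Step 4: simulated chance of at least one false positive** (n = 20, no true change, between-instrument correlation 0.5):

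| r | six rank-sum tests | one ANOVA per instrument | six signed-rank tests |
|---|---|---|---|
| 0.3 | about 10% | 2-3% | about 22% |
| 0.5 | about 4% | under 1% | about 22% |
| 0.7 | about 1% | under 0.1% | about 22% |

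Over between-instrument correlations of 0 to 0.7, the rank-sum figure runs from about 1% to 11% and the signed-rank figure from about 20% to 24%. The signed-rank column hardly moves with r because all three changes share one baseline: their covariance is σ²(1 − r) and their variance 2σ²(1 − r), so they correlate at 0.5 whatever r is. Counting only apparent improvement gives about 10-12%, and up to 13% if the instruments are uncorrelated.

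**Step 5: power cost, by illustration.** Take a shift of 0.6σ at one visit, with n = 20. This size is an assumption; the plan gives none.

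- Unpaired signal: 0.6 / √(2/20) = 1.90 standard errors. Simulated rank-sum power is about 41%.
- Paired signal: 0.6 × √20 / √(2(1 − r)) = 2.27, 2.68 and 3.46 at r = 0.3, 0.5 and 0.7. Simulated signed-rank power is about 55%, 70% and 89%.

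**Step 6: after a fix.** One instrument, one visit and one paired test: 5%. Both instruments at week 8, each at 0.05: 8-10%. Both at week 8, each at 0.025: 4.3-5.0%.

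**The case against.** The strongest reply is that this is a pilot. The plan disclaims power and says that all outcomes will be descriptive, so an argument about familywise error presumes a confirmatory claim that nobody makes. This carries weight, and it is why a descriptive-only analysis is an acceptable remedy. It does not remove the point. The descriptive sentence stands under the secondary heading, while the primary section prescribes tests and the secondary section prescribes them again. The text contradicts itself.

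Several stronger readings are tempting, and the documents do not support them.

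- *The plan carries a 20-24% false-positive rate.* That figure belongs to six paired tests that the plan does not name, at a significance level that it does not state, with any one result counting in either direction. The named tests give far less.
- *The comparison will be picked after seeing the data.* Only the choice of test is tied to the data. The visits to be compared are listed in advance; they are unranked, which is a different fault.
- *Either instrument suffices.* The wording could mean that both must improve. At the same visit, that would give a chance of about 1-5% with paired tests.
- *The NRS is a rival primary endpoint.* The sentence "Per individual a percentage improvement will be calculated as a main outcome" stands under the secondary heading and reads most naturally as the summary measure for that scale.

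**Conclusion.** The point holds as a defect of specification and of method. No instrument, visit, significance level or success rule is fixed, and the named tests do not suit repeated measurements on the same subjects.

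For the plan as written, the main cost is lost sensitivity. The familywise error of six rank-sum tests is about 1-11% and that of the omnibus ANOVA route under 3%, but power falls to about 41% where a paired test would have 55-89%. The low error rate is a by-product of the wrong tests and gives no protection once they are corrected: six paired tests with any one counting give about 20-24%.

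These sizes rest on an assumed two-sided 5% level, within-subject correlations of 0.3 to 0.7, normal scores, complete data on 20 subjects and, for power, an illustrative 0.6 SD shift. The mismatch between tests and design depends on none of these.

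**What to change.** Choose one of two routes.

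1. **One prespecified test.** In Primary study parameter(s), name one instrument and one visit in advance, for example the change in the Physician Assessment from baseline to week 8. The documents do not favour either instrument or any visit, so the choice is the sponsor's. Estimate the within-subject change with a 95% confidence interval and test it once by the Wilcoxon signed-rank test. Delete the clause that lets the distribution choose the test. Make the other instrument and the other visits descriptive. In Secondary study parameter(s), limit the descriptive-only sentence to the secondary outcomes and remove the tests listed there.
2. **Descriptive only.** Delete all the tests in both sections and report paired changes with 95% confidence intervals. This fits the pilot description in the sample size section.

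Either route is a change of wording, with no effect on visits, data collection or subject numbers. Under the first, an effect seen only at another visit or on the other instrument becomes exploratory. Under the second, the study reports no primary p-value.
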